8.0 SAFETY ANALYSIS

The safety data will include AEs, SAEs, clinical laboratory tests, and vital signs. Summaries will use the Safety all-risk population and will be presented separately for patients who received NKTR-214 and nivolumab or who received TKI (sunitinib or cabozantinib). Summaries using the Safety I/P-risk population may be presented. All safety data will be presented in data listings. Summaries for patients who received sunitinib and patients who received cabozantinib may be performed separately on some key safety analyses.

8.1 Adverse Events

Adverse events will be coded by system organ class (SOC) and preferred term (PT) using MedDRA. Adverse event severity will be based on NCI CTCAE Grade (version 5.0).

All AEs will be coded by MedDRA version 21.1. The severity of AE will be determined based on the National Cancer Institute Common Terminology Criteria for Adverse Events (NCI CTCAE) Grade (version 5.0). An AE is considered as related to treatment if it is related to any study drug; an AE with a missing relationship will be counted as related to study drug. An AE is considered as leading to treatment discontinuation if it is leading to discontinuation of any study drug. An AE is considered as leading to treatment delay, reduction or interruption if reported as leading to the dose delay, reduction or interruption of any study drug. An AE is considered as leading to death if the severity grade is 5 or the outcome is fatal. A patient reporting the same AE multiple times will be counted only once within each SOC and PT under the highest severity and closest relationship.

The following adverse events summaries will be provided by treatment arm:

- Overall summary of TEAEs
- TEAEs presented by worst grade (any grade, grade 3-4, grade 5) by SOC and PT
- Serious TEAEs presented by worst grade (any grade, grade 3-4, grade 5) by SOC and PT
- Drug-related TEAEs presented by worst grade (any grade, grade 3-4, grade 5) by SOC and PT
- NKTR-214-related TEAEs presented by worst grade (any grade, grade 3-4, grade 5) by SOC and PT
- TEAEs leading to any study drug discontinuation presented by worst grade (any grade, grade 3-4, grade 5) by SOC and PT
- TEAEs leading to infusion interruption of any study drug presented by worst grade (any grade, grade 3-4, grade 5) by SOC and PT
- TEAEs leading to dose reduction of any study drug presented by worst grade (any grade, grade 3-4, grade 5) by SOC and PT

- TEAEs leading to discontinuation of NKTR-214 presented by worst grade (any grade, grade 3-4, grade 5) by SOC and PT
- TEAEs leading to infusion interruption of NKTR-214 presented by worst grade (any grade, grade 3-4, grade 5) by SOC and PT
- TEAEs leading to dose reduction of NKTR-214 presented by worst grade (any grade, grade 3-4, grade 5) by SOC and PT
- Overall summary of TEAEs that required immune modulating medication by worst grade (any grade, grade 3-4, grade 5) by SOC and PT

Additionally, TEAEs will also be summarized in tables as follows:

- Grade 3 or above TEAE by PT
- Grade 3 or above drug-related TEAE by PT
- Grade 3 or above NKTR-214-related TEAE by PT
- Serious drug-related TEAE by PT
- Serious NKTR-214-related TEAE by PT
- Drug-related TEAE leading to discontinuation of any study drug
- NKTR-214-related TEAE leading to discontinuation of NKTR-214
- Drug-related TEAE leading to dose reduction of any study drug
- NKTR-214-related TEAE leading to dose reduction of NKTR-214
- Drug-related TEAE leading to death by PT
- NKTR-214-related TEAE leading to death by PT

The following analysis will be repeated using an extended treatment-emergent period.

- Drug-related TEAE presented by worst grade (any grade, grade 3-4, grade 5) by SOC and PT
- NKTR-214-related TEAE presented by worst grade (any grade, grade 3-4, grade 5) by SOC and PT

All AEs will be presented in listing as follows:

- SAEs
- Grade 3 or above TEAEs
- TEAE leading to any study drug dose delay
- TEAE leading to any study drug dose reduction
- TEAE leading to any study drug infusion interruption

- TEAE leading to any study drug discontinuation
- TEAEs leading to death

Overall summary of TEAEs and TEAEs by worst grade (any grade, grade 3-4, grade 5) presented by SOC/PT and treatment group will be provided for the following subgroups:

- Gender (Male, Female)
- Race (White, Black, Asian, Other)
- Age categorization (< 65, ≥ 65 years)
- Region (US, Rest of the world)
- Hepatic impairment at baseline (No [total bilirubin ≤ ULN and AST ≤ ULN], Yes [total bilirubin > ULN or AST > ULN])
- Renal impairment at baseline (No [creatinine clearance ≥ 60 mL/min], Yes [creatinine clearance < 60 mL/min])
- TKI Choice (sunitinib, cabozantinib)
- IMDC score (0 [favorable risk], 1-2 [intermediate risk], 3-6 [poor risk])

The subgroup analysis will be conducted using treatment-emergent period only.

8.2 Adverse Events of Special Interest for Checkpoint Inhibitors

8.2.1 Select Adverse Events (*to Support EU MAA*)

The select Adverse Events (select AEs, also known as select immune-related AEs) consist of a list of preferred terms grouped by specific category (e.g., pulmonary events, gastrointestinal events categories, etc.). Select AEs are identified based on the following 4 guiding principles:

- AEs that may differ in type, frequency, or severity from AEs caused by non-immunotherapies
- AEs that may require immunosuppression (e.g., corticosteroids) as part of their management
- AEs whose early recognition and management may mitigate severe toxicity
- AEs for which multiple event terms may be used to describe a single type of AE, thereby necessitating the pooling of terms for full characterization.

Based on these guiding principles and taking into account the types of AEs already observed across studies of nivolumab monotherapy, endocrinopathies, diarrhea/colitis, hepatitis, pneumonitis, interstitial nephritis, and rash are currently considered to be select AEs. Multiple event terms that may describe each of these are grouped into endocrine, gastrointestinal (GI), hepatic, pulmonary, renal, and skin select AE categories, respectively.

Hypersensitivity/infusion reactions are analyzed along with the select AE categories because multiple event terms may be used to describe such events and pooling of terms was therefore necessary for full characterization. Hypersensitivity/infusion reactions do not otherwise meet criteria to be considered select AEs.

The list of MedDRA preferred terms used to identify select adverse events is revisited quarterly and updated accordingly. The preferred terms used for the selection at the time of the database lock will be provided by categories/subcategories.

In addition to the frequency and worst severity of select AEs, time-to onset, time-to resolution, and time-to resolution where immune modulating medication was initiated will be analyzed for each specific category/subcategory of drug-related select AEs when applicable.

Further details on the definitions of select adverse event, time-to onset and time-to resolution are described in [Appendix 15.4](#).

Unless otherwise specified, analyses will be performed by select AE category. Analyses will also be repeated by subcategory of endocrine events.

8.2.1.1 Incidence of Select AE

Select AEs (also known as select immune related AEs) will be summarized using the treatment-emergent period by treatment arm for each category/subcategory.

- Overall summaries of any select AEs by worst CTC grade (any grade, grade 3-4, grade 5) presented by category or subcategory/PT
- Overall summaries of any drug-related select AEs by worst CTC grade (any grade, grade 3-4, grade 5) presented by category or subcategory/PT
- Overall summaries of any serious select AEs by worst CTC grade (any grade, grade 3-4, grade 5) presented by category or subcategory/PT
- Overall summaries of drug-related serious select AEs by worst CTC grade (any grade, grade 3-4, grade 5) presented by category or subcategory/PT
- Overall summaries of any select AEs leading to any study drug discontinuation by worst CTC grade (any grade, grade 3-4, grade 5) presented by category or subcategory/PT
- Overall summaries of drug-related select AEs leading to any study drug discontinuation by worst CTC grade (any grade, grade 3-4, grade 5) presented by category or subcategory /PT
- Summary of frequency of unique select AEs by category

A by-patient listing of select AE will be provided.

8.2.1.2 Time-to Onset of Drug-Related Select AE

Time-to onset of drug-related select AEs (any grade, grade 3-5) will be summarized for each category/subcategory by treatment arm. The summary is descriptive with median, min and max.

Time-to onset analyses are restricted to treated patients who experienced at least one drug-related select AE in the category/subcategory.

Additional details regarding the time-to onset definition are described in Appendix Section [15.4.1](#).

8.2.1.3 Time-to Resolution of Drug-Related Select AE

Time-to resolution of the following specific events will be summarized separately for each category/subcategory by treatment arm.

- Time-to resolution of drug-related select AE (any grade, grade 3-5)
- Time-to resolution of drug-related select AE (any grade, grade 3-5) where immune modulating medication was initiated

Time-to resolution analyses are restricted to treated patients who experienced the specific events. Time-to resolution where immune-modulating medication was initiated analyses are restricted to treated patients who experienced the specific events and who received immune-modulating medication during the longest select AE.

The following summary statistics will be reported: percentage of patients with resolution of the longest select AE, median time-to resolution along with 95% CI (derived from Kaplan-Meier estimation) and ranges.

Additional details regarding the time-to resolution definition are described in Appendix Section [15.4.2](#).

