For patients off treatment, the treatment-emergent period is defined as the period of time on or after the day (and time, if collected and not missing) of the first dose of study treatment, until: the date of (initiation of new anticancer therapy – 1 day) or (30 days after the date of the last dose of any study treatment), whichever is earlier.

The extended treatment-emergent period will be defined as the period of time on or after the day (and time, if collected and not missing) of the first dose of study treatment until earlier date of (initiation of new anticancer therapy – 1 day) and (100 days after the date of the last dose of any study treatment).

- **Treatment-Emergent Adverse Event (TEAE):**

TEAEs are AEs with an onset date (and time, if collected and not missing) within the treatment-emergent period, or extended treatment-emergent period depending on the analysis

Incomplete start and end dates for TEAEs will be imputed. Any AE will be considered as a TEAE if its status cannot be fully determined because of incomplete data.

- **Last Known Alive Date:** Last known alive date will be defined as the latest alive date on or before data cutoff date, captured from multiple sources. Note that if there is an event date (either an assessment or death) beyond the data cutoff date, the last known alive date will be the data cutoff date. If a patient died before or on the data cutoff date, the last known alive date will be set as the death date. The last known alive date will not be imputed, except in the case that the death date is partially missing (see details in Section 6.4)

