- Overall summary of non-endocrine IMAEs leading to study drug dose delay or reduction by worst CTC grade (any grade, grade 3-4, grade 5) where immune modulating medication was initiated presented by category / PT
- Overall summary of non-endocrine IMAEs leading to study drug dose delay by worst CTC grade (any grade, grade 3-4, grade 5) where immune modulating medication was initiated presented by category / PT
- Overall summary of non-endocrine IMAEs leading to study drug dose reduction by worst CTC grade (any grade, grade 3-4, grade 5) where immune modulating medication was initiated presented by category / PT
- Overall summary of endocrine IMAEs leading to study drug dose delay or reduction by worst CTC grade (any grade, grade 3-4, grade 5) presented by category / PT
- Overall summary of endocrine IMAEs leading to study drug dose delay by worst CTC grade (any grade, grade 3-4, grade 5) presented by category / PT

- Overall summary of endocrine IMAEs leading to study drug dose reduction by worst CTC grade (any grade, grade 3-4, grade 5) presented by category / PT
- Summaries of time-to onset and time-to resolution of non-endocrine IMAEs where immune modulating medication was initiated presented by category
- Summaries of time-to onset and time-to resolution of endocrine IMAEs presented by category.

A by-patient listing of IMAEs will be provided. By-patient listings of time-to resolution for longest IMAEs cluster (any grade and grade 3-5 in separate summaries) will also be provided.

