15.4.2 Time-to resolution definition

In order to derive the time-to resolution, overlapping or contiguous AEs within a specific category or subcategory will be collapsed into what will be termed “clustered” AEs. For example, if a patient (without pre-treatment AE) experienced an AE from 1st to 5th January, another AE (with different PT but within same category) from 6th to 11th January and same AE from 10th to 12th January, these will be collapsed into one clustered AE from 1st to 12th January. [Table 8](#) is summarizing key derivation steps for each type of clustered AEs.

Time-to resolution of AE (any grade) for a specific category is defined as the longest time from onset to complete resolution or improvement to the grade at baseline among all clustered AEs experienced by the patient in this category per adverse event criteria category. Events which worsened into grade 5 events (death) or have a resolution date equal to the date of death are considered unresolved. If a clustered AE is considered as unresolved, the resolution date will be censored to the last known alive date. Improvement to the grade at baseline implies that all different events in the clustered adverse event should at least have improved to the corresponding

(i.e. with same preferred term) baseline grade. This measure is defined only for patients who experienced at least one AE in the specific category.

The time-to resolution of AE (grade 3-5) for a specific category is defined similarly with an onset date corresponding to a grade 3-5 AE.

Time-to resolution of drug-related AE (any grade or grade 3-5) for a specific category is defined similarly but restricted to drug-related AE.

The time-to resolution of AE (any grade or grade 3-5, drug-related or all) where immune modulating medication was initiated is defined similarly. For data presentation not restricted to IMAE, the additional condition that the patient started an immune modulating medication during the longest AE resolution period will be applied.

Time-to resolution for a specific subcategory is defined similarly but restricted to event of this subcategory.

Table 8: Derivation of Clustered AE

Type of clustered AE	Derivation
Any grade	Collapse any on-treatment AE from the same category
Drug-related of any grade	Collapse any on-treatment drug-related AE from the same category

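### Resolution of select AEs is read from each patient's longest cluster only, so a shorter unresolved or fatal episode is not counted, and IMM-treated episodes drop out if a longer untreated one exists

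*SAP*

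**What the plan says.** SAP 15.4.2 merges overlapping or contiguous events in a category into clusters. A patient's time to resolution is then "the longest time from onset to complete resolution or improvement to the grade at baseline among all clustered AEs" that the patient had in the category. SAP 8.2.1.3 reports the "percentage of patients with resolution of the longest select AE, median time-to resolution along with 95% CI" from Kaplan-Meier, for any grade and for grade 3-5.

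On open or fatal episodes, 15.4.2 says: "Events which worsened into grade 5 events (death) or have a resolution date equal to the date of death are considered unresolved". It adds: "If a clustered AE is considered as unresolved, the resolution date will be censored to the last known alive date". SAP 6.6 fixes that date for patients who died: "If a patient died before or on the data cutoff date, the last known alive date will be set as the death date". A fatal cluster therefore has a length running from onset to death.

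The IMM version of the analysis in 8.2.1.3 is limited to patients "who received immune-modulating medication during the longest select AE". Section 15.4.2 repeats this condition, wording it as IMM started during the longest episode, and applies it only to presentations not restricted to immune-mediated AEs (IMAEs). SAP 8.2.2 also works from the longest cluster for IMAEs: "By-patient listings of time-to resolution for longest IMAEs cluster".

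**The concern.** Resolution status follows the one cluster that is longest, and nothing in the SAP ranks an unresolved cluster above a longer resolved one. An unresolved cluster contributes only the time observed so far. If that is shorter than an earlier resolved cluster, the unresolved cluster is never selected and the patient enters as a resolution event. Yet the quantity defined is a maximum over clusters; while one cluster is open, the maximum is known only to be at least the longest duration seen.

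The IMM condition has a related flaw. Whether a treated episode is analysed depends on its own length relative to the patient's other episodes in the category, so inclusion depends on the outcome being summarised.

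At stake is the description of how reversible immune-related toxicity is. SAP 8.2.1 is labelled as supporting the EU application. Repeat episodes are foreseeable: Protocol 5.13.7 lets dosing resume once an event has settled, Protocol 5.14.1.1 provides for events that recur, and Protocol 5.13.4 describes transient transaminase rises mainly in Cycles 1 and 2. Skin and hepatic events are both select-AE categories.

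**Working it through.** **The SAP's own example.** Applying the collapsing conventions of 15.4.2 to events on 1-5, 6-11 and 10-12 January gives one cluster from 1 to 12 January, as the SAP states.

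**Worked patients.** Both end days are counted; unresolved clusters run to the last known alive date.

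| Case | Clusters in one category | Longest | Result under the SAP |
|---|---|---|---|
| A | Days 20-79 resolved (60 d); days 150-159 fatal (10 d) | 60 d | Resolved |
| B | Days 20-79 resolved (60 d); open from day 150, last known alive day 180 (31 d) | 60 d | Resolved |
| B, longer follow-up | As B, last known alive day 400 (251 d) | 251 d | Unresolved |
| C | Days 20-26 with steroid (7 d); days 100-159 untreated (60 d) | 60 d | Excluded from IMM analysis |
| D | Days 20-79, then fatal event from day 80 to day 90, merged (71 d) | 71 d | Unresolved |
| E | Days 20-26 with steroid, no other episode (7 d) | 7 d | Kept in IMM analysis |

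**Direction.** A patient whose clusters all resolved is always counted as resolved. The reported percentage is therefore never below the percentage with complete resolution.

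**Size of the resolution part.** All rates here are assumptions. Let f be the share of patients with two separate clusters, u the probability that the last one is unresolved, and p the probability that the resolved cluster is longer than the observed part of the unresolved one. Then

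overstatement = f × u × p, with p = mean resolved / (mean resolved + mean observed) for exponential times.

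- With a mean resolved duration of 60 days, p = 60/(60+180) = 0.25, 60/(60+60) = 0.50 or 60/(60+20) = 0.75, for mean observed times of 180, 60 or 20 days.
- Low end: 0.10 × 0.10 × 0.50 = 0.5 points. Simulation with 30-day medians for all durations gave 90.5% reported against 90.0% with all clusters resolved.
- Middle: 0.30 × 0.30 × 0.50 = 4.5 points. Simulation gave 74.5% against 69.9%.
- High end: 0.40 × 0.40 × 0.75 = 12 points. This needs frequent recurrence, many open episodes and short observation.

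**Size of the IMM part.** Suppose each cluster has a 50% chance of IMM and all durations have the same distribution. Among patients with any treated cluster, the share dropped is 0.25f / (0.5 + 0.25f):

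- f = 0.10: 0.025/0.525 = 4.8%
- f = 0.30: 0.075/0.575 = 13.0%

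Simulation gave 4.7% and 13.0%.

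**Kaplan-Meier median.** The obvious repair is to censor the affected patients at their longest observed duration. A simulation assumed exponential times with a 56-day median, 40% of patients with two clusters and mean observation of 180 days:

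| Never resolving | True median | SAP rule | Censored instead |
|---|---|---|---|
| 10% | 84.3 d | 81.9 d | 89.1 d |
| 25% | 109.5 d | 101.3 d | 115.5 d |

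The SAP rule is too short and the censored version too long. Neither is closer in both settings.

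**The case against.** The statistic is labelled for what it is: resolution of the longest event, not of all events. It misleads only when a patient has at least two non-contiguous clusters in one category and the resolved one is longer. Contiguous episodes merge (case D). For survivors, the last known alive date moves on with the 12-weekly survival contacts, so an open episode tends to become the longest (case B with longer follow-up). All of this stands, and it limits the size without removing the effect.

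A reader might infer that fatal immune-related events disappear from the safety report. They do not. Grade 5 select AEs stay in the incidence tables and listing (SAP 8.2.1.1), drug-related events leading to death are tabulated (8.1), and deaths are summarised (8.4). Those outputs do not, however, correct the resolution percentage.

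A reader might also infer that most steroid-treated episodes are lost. For patients with exactly one treated and one untreated cluster, with exponential medians of 21 and 42 days, 42/(21+42) = 67% of treated episodes are excluded, and those kept have a median of 42 days. That describes only this subgroup; a sole short treated episode is always kept (case E). In the grade 3-5 table, Table 8 of the SAP removes clusters with no grade 3-5 record, so a long mild rash cannot displace a short treated grade 3 rash. Non-endocrine IMAEs must by definition have been treated with IMM (8.2.2), so the IMAE summaries do not share the IMM problem.

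Finally, the two parts do not both flatter Arm A: the first raises the resolution percentage, while the second lengthens the IMM median.

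**Conclusion.** The point holds in limited form. As written, a patient with a longer resolved cluster and a separate, shorter unresolved or fatal one is reported as resolved, and the percentage can only overstate complete resolution. The documents supply no recurrence, resolution or follow-up rates for these events, so the size is not computable from them. The range of about 0.5 to 12 percentage points rests on 10-40% of patients having two clusters, 10-40% having an unresolved last episode, and p from 0.50 to 0.75. The effect comes mainly from second episodes that are rapidly fatal or start near the data cutoff. In the grade 3-5 table, only another grade 3-5 cluster can hide a fatal one.

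The IMM condition selects on episode length, mainly in the any-grade select-AE table, and pushes that median upward. About 5-13% of IMM-treated patients drop out under the equal-duration assumption above.

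The documents do not support reading this as concealment of deaths or as a threat to any efficacy conclusion. The analysis is descriptive and touches no alpha, power or endpoint.

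**What to change.** In SAP 8.2.1.3 and 15.4.2:

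1. Classify a patient as resolved in a category only if every cluster in that category resolved, and report that percentage. Apply the same rule to the IMAE time-to-resolution summaries in 8.2.2.
2. For the select-AE IMM analysis, take the longest cluster among those in which IMM was started, instead of requiring IMM during the overall longest cluster.
3. For the Kaplan-Meier median, show the result with patients who have any unresolved cluster censored at their longest observed duration, beside the longest-cluster result. State that the first tends to be too long and the second too short.

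The cost is a few sentences in the SAP, minor programming and one extra column. The reported resolution percentage may become slightly less favourable. No data collection or trial conduct changes.
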